1. BACKGROUND

1.1 Summary and Study Design

The goal of the study is to provide a high-intensity exercise program for older Veterans that can be widely disseminated and attenuates processes underlying aging. The study is a randomized trial of 12-weeks of high-intensity functional circuit exercise that will be broadcasted from the Salem VAMC to older Veterans living with HIV in the Atlanta and Baltimore VAMCs. Our primary objective is to determine the effect of VTEL exercise compared to sedentary controls on cardiorespiratory fitness, anaerobic threshold, and O₂pulse based on gas exchange at peak exercise (Aim 1) in addition to sarcopenia and frailty (Aim 2). We also will investigate the effect of VTEL exercise on DNA methylation as a biomarker of advanced aging and determine correlates with biomarkers of systemic inflammation (Aim 3). The sedentary control group will be offered the 12-week exercise training and follow-up testing in a delayed entry design to ensure equity of the benefits of exercise to all participants.

1.2 Rationale and Significance

Treated HIV infection is a chronic disease with numerous elements of biological aging and age-related conditions that are advanced or accelerated.¹⁻⁴ Not surprisingly, adults living with HIV (HIV+ adults) have an increased risk of disability with reduced cardiorespiratory fitness⁵ and increased sarcopenia⁶. The VHA is the largest U.S. HIV health provider with 64% of these Veterans 50+ years of age.⁷ Effective and feasible exercise rehabilitation programs are needed to prevent widespread disability in these Veterans. Our findings and the work of others support the argument that higher intensity exercise may be needed to reverse the putative mechanisms of aging.⁸⁻¹¹ Our goal is to provide a high-intensity exercise program for older Veterans that can be widely disseminated and attenuates processes underlying aging.

Effective strategies for high-intensity exercise in older adults remain a challenge.¹² Circuit exercise, which involves quick transitions between exercises, is a high-intensity training approach that can increase cardiorespiratory fitness (VO₂peak) and strength in adults 65+ years of age^{13,14} but has yet to be tested in HIV+ adults. At the Salem and Baltimore VA Medical Centers (VAMCs), Veterans 65+ years of age participate in a center-based exercise program, Gerofit, that increases endurance and strength.¹⁵⁻¹⁷ We recently converted Gerofit into video telehealth (VTEL) circuit exercise classes that are functional (no stationary equipment), yet improve endurance and strength. The objective of this project is to adapt our center-based high-intensity aerobic (AEX) and resistance training (RT) intervention in older HIV+ Veterans into a VTEL-delivered high-intensity circuit exercise program that has the potential for large-scale implementation into VAMCs nationwide.

With increasing age, epigenetic alterations occur that affect transcription in reproducible patterns of DNA methylation (DNAm).^{18,19} DNAm Age is an estimate of epigenetic age based on 353 methylation sites which Horvath derived and validated in diverse populations and multiple tissues.²⁰ DNAm Age is expressed in units of years that can be compared to chronologic age, thus providing a concrete measure of advanced aging. Recent molecular studies support DNAm Age as a comprehensive biomarker of advanced aging.²¹ We and others found that HIV+ adults have increased DNAm Age compared to age-matched adults without HIV.^{22,23} In adults without HIV increased DNAm Age is associated with physical inactivity,^{24,25} weakness²⁵ and frailty.²⁶ Our preliminary data show that DNAm Age correlates with the VACS Index,²⁷ a measure of frailty in HIV+ adults. However, the impact of exercise training on DNAm Age has yet to be determined in any patient population.

In observational studies of HIV+ adults, systemic inflammation independently predicts cardiovascular events,²⁸ sarcopenia, and frailty.²⁹ However, the anti-inflammatory response to exercise varies in HIV+ adults, likely affected by comorbidity and lifestyle factors.³⁰⁻³³ Methylation profiles in candidate genes have been identified that are associated independently with aging phenotypes (age-related diseases, frailty)³⁴ and lifestyle factors (smoking, physical activity).^{35,36} Many of these candidate

genes encode pro-inflammatory cytokines.³⁷ Further, randomized exercise trials demonstrate epigenetic changes that downregulate pro-inflammatory cytokines.³⁸⁻⁴¹ Significant methylation changes in DNA isolated from blood leukocytes can occur after acute exercise⁴² and only 8 weeks of training.⁴³ Yet, the effect of exercise on methylation in HIV+ adults is unknown.

This study leverages our exercise training experience in HIV and VTEL, availability of 3,000 HIV+ Veterans at Atlanta and Baltimore VAMCs, and the VA VTEL infrastructure. Results will impact the fields of exercise rehabilitation, HIV, and aging and can be rapidly implemented using existing resources. Exercise-mediated changes to methylation provide a pre-clinical benchmark that demonstrate anti-aging effects of exercise. Epigenetic driven exercise strategies could play a valuable role in precision medicine.

1.3 Hypothesis and Study Aims

The overarching hypothesis is that VTEL high-intensity functional circuit exercise in older HIV+ Veterans will improve the advanced aging phenotype and attenuate DNAm epigenetic processes underlying aging. We will explore the use of DNAm Age as an innovative biomarker that can predict adaptation to exercise by testing its association with exercise outcomes. Our experimental approach includes a 12-week VTEL exercise intervention in 80 older HIV+ Veterans who are randomized to exercise or standard of care sedentary control groups with the specific aims:

AIM 1. To determine the effect of VTEL exercise compared to control on:

- 1.1 Cardiorespiratory fitness, anaerobic threshold, and O₂pulse based on gas exchange at peak exercise
- 1.2 Sarcopenia defined by the European Working Group on Sarcopenia⁴⁴
- 1.3 Frailty defined by the Fried Phenotype⁴⁵ and the Veterans Aging Cohort Study (VACS) Index²⁷

AIM 2. To investigate the effect of VTEL exercise on DNAm Age²⁰ as a biomarker of advanced aging

AIM 3. To determine the effect of VTEL exercise on systemic inflammation by measure of:

- 3.1 DNA methylation of genes encoding pro-inflammatory cytokines in leukocytes (transcriptional regulation)
- 3.2 Corresponding systemic levels of pro-inflammatory cytokines IL-6 and IL-18 (protein expression)

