Phenotypic Outcomes (AIM 1) and Biomarker DNA Age (AIM 2): We hypothesize that the VTEL high-intensity circuit exercise intervention will increase cardiorespiratory fitness and decrease sarcopenia and frailty (AIM 1) and decrease DNA Age (AIM 2). ANOVA models will be used with dependent variables of cardiorespiratory fitness (VO₂peak, 2-minute step test) and DNA Age (years). Logistic or multinomial models will be used with dependent variables of sarcopenia (present/not present) and frailty (robust/pre-frail/frail). Secondary analyses will be performed that use the individual components of composite outcome as their own dependent variable (e.g., lean mass and strength from sarcopenia). ANCOVA will be used to test for between group difference by time (pre/post exercise). Baseline performance and demographic and clinical characteristics will be included in models to assess and adjust for known potential confounding factors based on our experience with older HIV+ adults. We do not expect significant variability or effect from HIV-related factors (e.g., antiretroviral therapy, viral load) since we will use our previous established eligibility criteria. We do not anticipate needing to adjust for sex or race since each individual will function as their own control. Nutritional analyses of macro and micronutrients will be performed to measure any change during the study, and if present, will be tested for within group and between group effects. A similar approach will be applied to smoking exposure, which will be quantitated at baseline and follow-up testing. Treatment fidelity will be measured as percent of AEX time at target heart and entered in ANOVA models. For future planning, feasibility analyses will include calculation of rates for enrollment, retention, and attendance overall and by HIV group. Aggregate data will be collected on adverse events and reasons for lost to follow-up.

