Analyses will include participants who drop out before completion of the 12-week intervention period by way of multiple imputation. This intention to treat approach will investigate factors that may affect compliance and difficulty with exercise training, including soreness and medical comorbidity. If the pattern of missing data is missing completely at random, or simply at random, our multiple imputation should eliminate bias due to loss to follow-up. Because the participants will be recruited from clinic-based VA cohorts, we will be able to obtain clinical data from participants who drop out of the study, but remain in clinical care, to determine if drop-out was related to medical conditions that may influence outcomes. Thus, we will be able to estimate bias introduced by loss to follow-up. If there is sufficient information, we may be able to model the drop-out process and adjust our analyses for loss to follow-up even if the missing data pattern is non-ignorable. If 36 training sessions cannot be completed in 12 weeks, then total training time will be tracked, and incorporated into the data analysis.

DNA Methylation (AIM 3): We will examine the change of methylation levels after 12 weeks for each candidate marker using ANOVA models. To examine epigenetic association with each outcome, we will fit the linear regression model as follows: where Y_i is the quantitative outcome measurement, Z_i is the vector of covariates including age, race, smoking status and leukocyte proportions, and E_i is the candidate epigenetic marker. ANCOVA will be used to test for between group difference by time (pre/post exercise). The candidate epigenetic markers will involve individual CpG sites previously identified and discussed in detail section D4c. We will extend this linear regression model to account for batch/chip effects and

longitudinal measures using a linear mixed model. We will adjust the significance threshold for multiple testing using Bonferroni correction ($p < 0.05 / \text{number of tests}$).

Sample Size Estimates:

AIM 1. Paired t-test was used to test for a mean change given a range of correlation between pre and post values with assumptions of $\alpha = 0.05$ and 80% power. (Mean (SD) values for the VO_2peak are from our current high-intensity AEX + RT trial in HIV+ Veterans (Table 3). Data for 2-minute step test are from our VTEL Gerofit exercise program (C3). Values for chair stands are results from a 10-week RT in older men.⁴⁶ We will have adequate

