Two-minute step test (2-MST): Rationale: Cardiopulmonary exercise testing will not readily be available when the VTEL exercise program is translated to clinical care. The 2-MST correlates with VO_2 peak in older patients ($r=0.33$; $p<0.01$)⁷³ and is advocated as a surrogate measure of aerobic capacity in space limited settings⁷² Method: The test will be performed according to the Rikli and Jones protocol in which the number of times the right knee reaches a pre-determined height is counted in 2 minutes.⁷¹ The test-retest reliability is 0.88.⁷² As a secondary analysis, we will correlate the 2-MST with VO_2 peak, not previously reported in HIV+ adults.

Frailty:

Frailty phenotype: The frailty phenotype by Fried et al. will be used to measure frailty phenotype.⁷⁴

Rationale: The Fried frailty phenotype has been widely studied in HIV+ adults.⁷⁵ **Method:** The five domains of the phenotype (slowness, weakness, low activity, weight loss, and exhaustion) will be measured and scored as previously described.⁷⁴

VACS Index: Based on our research in the Veterans Aging Cohort Study (VACS)⁷⁶ and recent epigenetics literature,⁷⁷ the VACS Index will be calculated²⁷ and used as a secondary measure of frailty. The VACS Index will be calculated based on clinically available lab values, such as kidney and renal function, age, and CD4 cell count and HIV-1 RNA level (viral load).²⁷

Blood Sampling: Blood collection, storage, and testing will be performed in the Baltimore and Atlanta VAMC laboratories. The samples will be collected across multiple draws. One of the blood draws will be conducted after an overnight fast. Staff will attempt to phlebotomize the patient during the approved fasting DXA visit to minimize discomfort and inconvenience to the patient. Blood samples will be collected in appropriate tubes using established protocols per the planned assays. Plasma will be immediately separated by centrifugation at 4°C, aliquoted, then frozen at -80°C and stored until further processing and analysis. Pre/post intervention samples from the same participant will be analyzed in the same assay.

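### The exploratory objective that DNAm Age predicts adaptation to exercise has no model and no arm-by-DNAm Age term, so a bare association could not separate prognosis from response to exercise

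*Combined protocol and SAP*

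**What the plan says.** Section 1.3 sets out an exploratory objective and its method in one sentence: to "explore the use of DNAm Age as an innovative biomarker that can predict adaptation to exercise by testing its association with exercise outcomes". It does not say whether the predictor is DNAm Age at baseline or its change, which arm or arms are used, or which covariates enter.

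The Statistical Plan (2.3.e) does not return to it. The relevant content there is:

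- **DNAm Age as an outcome.** For Aims 1 and 2, "ANOVA models will be used with dependent variables of cardiorespiratory fitness (VO₂peak, 2-minute step test) and DNA Age (years"). No model has it on the right-hand side.
- **Adjustment in Aims 1 and 2.** "Baseline performance and demographic and clinical characteristics will be included in models to assess and adjust for known potential confounding factors". Chronological age is not named. The next remarks on adjustment concern other variables: "We do not anticipate needing to adjust for sex or race since each individual will function as their own control".
- **The only outcome-on-marker regression.** It sits under Aim 3, where "Z_i is the vector of covariates including age, race, smoking status and leukocyte proportions, and E_i is the candidate epigenetic marker". Age is listed; arm and arm by marker are not. Its scope is narrower than DNAm Age: "The candidate epigenetic markers will involve individual CpG sites previously identified".
- **Group comparisons.** The stated test is arm by time (pre/post), not arm by biomarker.

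On scale, section 1.2 says "DNAm Age is expressed in units of years that can be compared to chronologic age". No age-acceleration variable is defined.

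**The concern.** Predicting adaptation to exercise means that the exercise-minus-control effect differs according to baseline DNAm Age. An association between DNAm Age and outcome does not show this. People with lower DNAm Age may do better over 12 weeks with or without exercise, and that would produce the same association. Restricting to the exercise arm does not help, because it discards the randomised comparator that would reveal the difference.

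The second issue is chronological age. DNAm Age is an estimate of age in years, eligibility is 50 and over with no stated upper limit, and age is itself an input to one of the frailty measures: "The VACS Index will be calculated based on clinically available lab values, such as kidney and renal function, age, and CD4 cell count". If chronological age is not handled, an apparent DNAm Age effect may be no more than the effect of birth date.

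What is at stake is the interpretation. Section 1.2 links this work to precision medicine, and a prognostic association could be read as showing who benefits from exercise.

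**Working it through.** **1. The plan's own DNAm Age figure.** Inputs (2.3.e, sample size table): pre 62 (SD 10.8), post 68.7 (SD 10), so the difference is 6.7; alpha 0.05, 80% power, paired t-test.

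SD of the difference = √(10.8² + 10² − 2·r·10.8·10):

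- r = 0.3: √151.84 = 12.32
- r = 0.5: √108.64 = 10.42
- r = 0.7: √65.44 = 8.09

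A two-sided paired t-test (noncentral t) gives n = 29, 21 and 14, exactly as printed. These sizes concern a mean change within one group. No size or power is given for the prediction objective.

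**2. Association against interaction.** Simulated trials (2,000 per setting, ordinary least squares) in which DNAm Age relates to outcome change *equally in both arms*, so it does not predict response to exercise. The standardised slope (0.3 or 0.5) is assumed; the documents give none. N = 80 is the randomised number (3.1); N = 56 is 80 × 0.70, from the 30% attrition in 3.3.a.

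| Share of trials with p < 0.05 | N = 56 | N = 80 |
|---|---|---|
| Pooled association, slope 0.3 | 57–58% | 74–75% |
| Pooled association, slope 0.5 | 93–95% | 98–99% |
| Arm-by-marker interaction | 4–5% | 5–6% |

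For the exercise arm alone (m participants), the normal approximation is Φ(slope × √m − 1.96). With m = 28 it gives 35% (slope 0.3) and 75% (slope 0.5); with m = 40, 48% and 89%. Both forms of association are often significant when exercise response does not depend on the marker.

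**3. Chronological age.** Simulated trials in which *only chronological age* modifies the exercise effect (assumed slope 0.3–0.5; assumed DNAm Age to age correlation 0.6–0.9).

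| Test | Share with p < 0.05 |
|---|---|
| Raw DNAm Age, exercise arm | 14–56% (N = 56); 21–76% (N = 80) |
| Same, with age as covariate | 4–6% |
| Raw DNAm Age × arm, no age term | 10–47% |
| Raw DNAm Age × arm, age as main effect only | about 10–47% |
| Age acceleration × arm, with age | about 4–6% |

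An interaction on raw DNAm Age therefore does not cure the age problem, even with age as a main effect. Using the residual on age does.

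**4. Power of the proper test.** With marker and residual SD set to 1, the standard error of the slope difference is √(2/m) per arm of size m. The smallest difference detectable with 80% power is (1.960 + 0.842) × √(2/m):

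- m = 40: 2.802 × 0.2236 = 0.63
- m = 28: 2.802 × 0.2673 = 0.75

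For slope differences of 0.3, 0.4 and 0.5, power is 27%, 43% and 61% with 40 per arm, or 20%, 32% and 46% with 28 per arm.

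**The case against.** The strongest reply is that the plan has not chosen a wrong analysis; it has not described one. The sentence in 1.3 says explore, the objective is not among Aims 1 to 3, and nothing commits to an unadjusted test of raw DNAm Age. Section 2.3.e plans demographic adjustment for Aims 1 and 2, the nearest regression lists age, and section 1.2 discusses DNAm Age relative to age-matched adults. With age in a linear model, raw DNAm Age and its residual give the same main-effect coefficient. All of this stands: age handling is unstated, not ruled out.

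A reader might infer that the trial will report an age artefact as a finding, and might try to size this. If DNAm Age correlates 0.8 with age (assumed), the induced correlation is 0.8 × r(outcome, age), and by Fisher's z the chance of p < 0.05 at n = 80 is 57%, 83% and 96% for r = 0.3, 0.4 and 0.5. Those values of r suit outcome *levels*. Adaptation is *change*, and with r = 0, 0.1 and 0.2 the figures are about 5%, 11% and 29% (5%, 8% and 17% at n = 40). The documents give no age-change correlation, so the high range is not a result about this trial. The VACS Index argument also weakens for change, since everyone ages equally over 12 weeks.

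The reply does not reach the interaction. Adjusting for age does not turn a prognostic association into effect modification.

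**Conclusion.** The point holds as a gap in specification with a definite consequence. Section 1.3 names association as the method, 2.3.e supplies no model, and no arm-by-DNAm Age term exists. Followed as written, the method could support a conclusion about response to exercise that the evidence does not bear. The 57–99% pooled rates in the working illustrate this under assumed slopes of 0.3 to 0.5; the logic does not depend on the exact values.

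Two stronger readings are not supported. The documents do not plan an unadjusted raw DNAm Age test; they are silent on age for this analysis. Nor is the question beyond the trial: the randomised control arm allows the right test, though with low power. As the objective is exploratory, this is a cheap improvement and does not threaten the main aims.

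**What to change.** Add a short paragraph to 2.3.e for this objective:

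- **Predictor:** baseline DNAm age acceleration, defined as the residual of DNAm Age on chronological age.
- **Model:** both arms together; follow-up outcome on baseline outcome, chronological age, arm, acceleration, and arm × acceleration.
- **Interpretation:** any statement that DNAm Age predicts adaptation rests only on the interaction estimate and its confidence interval, labelled exploratory. Main-effect associations are reported as prognostic.

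The cost is wording only. Arm, age, baseline DNAm Age and the outcomes are already to be collected. The downside is low power (about 20% to 61% for slope differences of 0.3 to 0.5, across 28 to 40 per arm), so the likely result is a wide interval and a more cautious statement. The plan should say so in advance, so that a non-significant interaction is not read as evidence of no difference.

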2 STUDY STRUCTURE AND GOVERNANCE

2.1 Overview

The Salem VAMC (SVAMC) will function as the coordinating site under direction of the contact PI ([name]) for the primary multi-PI Merit award (I01 RX002790, [name]/[name]/[name]). Atlanta (AVAMC) and Baltimore (BVAMC) will function as the participant enrollment sites. SVAMC research staff will lead the exercise intervention which will be provided by VTEL broadcast to designated telehealth rooms located at Atlanta and Baltimore VAMCs which are supervised by local research staff. The study responsibilities and activities of each of the three medical centers is summarized in Table 1 below. Guidance for each research activity is provided in a single study *Manual of Operations* which is based on the Merit Award and written by the PIs ([name]/[name]/[name]). The purpose of the Manual of Operations is to ensure scientific rigor and consistency of study activities across enrollment sites and thus attainment of study scientific aims. The Manual of Operations will refer to a specific *Standard Operating Procedure (SOP)* for each research procedure. The coordinating site will provide the template for each SOP to the enrollment sites. The enrollment sites are responsible for site-specific changes to SOPs, e.g., location and local oversight, and obtaining local regulatory approval (IRB and R&D) for

conduct of all research activities at their site. The coordinating site is responsible for all data management and analysis, and overall scientific integrity of the study.

Table 1. Roles & Responsibilities by Site	Salem	Atlanta	Baltimore
Recruitment, Consent, and Enrollment		X	X
Randomization	X		
Baseline and follow-up testing		X	X
Exercise intervention	X		
Data collection		X	X
Data management and analysis	X		
Blood testing and banking for future testing		X	X

2.2 Communication Plan

2.2.a Roles and Responsibilities

Drs. [name], [name], and [name] will provide overall scientific leadership for this study and are ultimately responsible for coordinating investigations and activities, for ensuring integrity of the scientific work, and for monitoring budgetary expenditures. They will share administrative responsibilities for the scientific management of this project and meeting the requirements of all regulatory boards (Institutional Review Boards and Research and Development Committees at Atlanta, Baltimore, and Salem VAMCs). As the contact PI of the Merit Award, [name] will be responsible for: a) meeting study benchmarks; b) coordination of data collection and quality assurance; c) interpretation of data and data analysis; and d) preparation of manuscripts, presentations, and progress reports. [name] will have a primary role in conduct of the VTEL exercise intervention, which will be broadcast from the Salem VAMC. She will supervise all Salem VAMC study staff. [name] will be the site PI at the Atlanta VAMC (i.e., PI on the Atlanta VAMC IRB protocol). He will have the primary role of participant recruitment, retention, completion of planned testing, and data collection at the Atlanta VAMC. He will supervise the study staff at the Atlanta VAMC. He will also facilitate collaboration with Atlanta VAMC co-investigators and oversee laboratory analyses conducted at the Atlanta VAMC, including sample collection, handling, processing, storage and assays. [name] will be the site PI at the Baltimore VAMC (i.e., PI on the Baltimore VAMC IRB protocol). [name] will have the primary role of participant recruitment, retention, completion of planned testing, and data collection at the Baltimore VAMC. Of note, since [name] move to the Salem VAMC, [name] has been functioning in this capacity for their RR&D Merit Award (I01 RX000667, [name]/[name]), which includes Baltimore site participants in addition to those enrolled at the Salem VAMC. She will supervise the study staff at the Baltimore VAMC. She will oversee laboratory analyses conducted at the Baltimore VAMC, including sample collection, handling, processing, storage and assay of biomarkers, and shipping of samples to the DNA methylation laboratory in Atlanta.

2.2.b Investigators

To ensure close communication, Drs. [name], [name], and [name] will have standing scheduled conference calls which may also include each site's research coordinator. During the initial study implementation period (first 3-6 months), calls will occur weekly and then as needed. Monthly teleconferences will occur using the VTEL research rooms throughout the 4- year study period and will include all PI's and key staff. The purpose of the monthly VTEL meetings will be to monitor study benchmarks and for ongoing problem solving. The research team will review any important revisions to procedures and ensure that protocol fidelity is maintained across all sites. Drs. [name], [name], and

[name] will have at least one in-person meeting annually to discuss plans for data analysis, presentations, publications, and future grant applications. Collaborators will be included. Support for this travel is included in the budget. [name] already routinely travels to Baltimore to meet with [name] and other collaborators. Drs. [name] and [name] will continue to participate in monthly VACS-related conference calls, including the steering committee and the Physical Function Working Group calls. In the unlikely event that conflict would arise related to the current proposal, Drs. [name], [name], and [name] have several mutual resources and colleagues in the VACS and Gerofit networks. These individuals would help resolve any disputes related to this project.

2.2.c Staff Coordination and Training

Informal regular calls, emails and interactive Skype calls (shared computer screen) will occur among the research staff in addition to the formal monthly research team meetings. The program coordinator will be available daily for the research coordinators and will also facilitate communication with the exercise physiologist and data manager. As is currently routine for [name] research team, the program coordinator will meet regularly with the data manager to discuss QA/QC issues. [name] will meet weekly with the exercise physiologist to ensure intervention fidelity and discuss any safety issues. [name] and the program coordinator meet daily. Similarly, Drs. [name] and [name] have established research teams at each of their sites with coordinators located within the unit who can meet with them daily as needed.

Coordination of study activities across the three sites will be ensured by using experienced research personnel with well-defined roles, as summarized in Table 2 below. All the research staff involved in the research will also fulfill the VA and NIH guidelines for ethical conduct of research and good clinical practice. Investigators and study staff will receive ongoing training in research ethics and good clinical practice to fulfill all requirements of the VA and local policy. A site visit will be performed by [name] and the program coordinator during start-up, and as needed during the project, to provide training on the manual of operations and standard operation procedures. These project-related documents as well as the case report forms (CRFs) will be located on the study's network research folder and available at all time to all research staff. The program coordinator and data manager will provide ongoing education to the enrollment sites as part of their routine duties at Salem.

Table 2. Research Staff for Project

Title/role	Location and effort	Description
Research coordinator	Atlanta VAMC (100%)	Responsible for the daily management of the study at the enrollment site which includes: 1) recruitment and screening of participants; 2) providing informed consent; 3) scheduling all testing and training visits; 4) completion of case report forms; 5) management of participant reimbursements; 6) maintenance of recruitment and retention statistics; 7) reporting and correspondence to regulatory and oversight committees; 8) maintenance of the regulatory study binder and participant research folders; 9) performing quality assurance of all study activities in coordination with the data manager.
Research coordinator	Baltimore VAMC (100%)	Responsible for the daily management of the study at the enrollment site which includes: 1) recruitment and screening of participants; 2) providing informed consent; 3) scheduling all testing and training visits; 4) completion of case report forms; 5) management of participant reimbursements; 6) maintenance of recruitment and retention statistics; 7) reporting and correspondence to regulatory and oversight committees; 8) maintenance of the regulatory study binder and participant research folders; 9) performing quality assurance of all study activities in coordination with the data manager.
Program coordinator	Salem VAMC (50%)	Responsible for overall oversight of the project which includes: 1) monitoring numbers for recruitment, enrollment, and completion; 2)

		maintenance of current Manual of Operations; 3) providing template SOPs and CRFs to enrollment sites; 4) coordinating calls and meetings; 5) conducting audits of CRFs and protocol deviations to assess and correct inconsistencies between sites and coordinators; 6) reporting and correspondence to Salem VAMC regulatory committees; 7) maintenance of the Salem protocol regulatory study binder
Exercise physiologist	Salem VAMC (50%)	1) conduct VTEL exercise per protocol; 2) instruct and supervise participants during all exercise sessions, including maintenance of exercise training logs and HR data; 3) coordinate VTEL classes with staff at AVAMC and BVAMC
Data manager	Salem VAMC (25%)	1) oversee data collection and entry, including data QA/QC; 2) design and maintain databases located on Salem VAMC server and VINCI (REDCAP); 3) conduct data analysis and generate tables and figures

